4.1.3 Per-Protocol (PP) Population

The per-protocol population includes all patients who completed both treatment sequences with no major protocol violations.

4.1.4 Populations Used for Analyses

The primary effectiveness analysis will be based on the ITT population. Sensitivity analyses of the primary effectiveness endpoint will be generated based on the PP population.

The demographics and baseline characteristics will be based on ITT Population.

The safety analysis will be based on the Safety population.

All secondary effectiveness analyses will use ITT population , with sensitivity analyses using the PP population (similar to the primary effectiveness analysis).

4.2 Data Handling Conventions

4.2.1 Missing Data

- Any blank value will be treated as missing (unknown)
- Blank values will be left as blank in the data listings.
- Missing data will not be imputed unless specified

4.2.2 Per Protocol Time Points Vs Actual Time Points

Actual time points will be used for the all parameter calculation unless otherwise specified. Per protocol time may be used if the by each time point summary is needed.

4.2.3 Inconsistent Time Points between CRF and Lab Transferred Data

N/A.

4.2.4 Repeated and Unscheduled Visit

4.2.4.1 Repeated Visit

A repeated visit is defined as a visit done at different date/time but is considered the same visit by the study site.

The principle of 'last observation priority' will be used to handle the situation of repeated visits unless there is a specific instruction from the study site. There are some general recommendations:

- If a variable (except dates and all lab transferred data) is newly measured/collected at the repeated visit, the value of that variable will be replaced with the value from the repeated visit.
- Dates and lab transferred data will be determined case by case based on their medical importance/meaning.
- If a variable is not measured/collected at the repeated visit, then the value from the original visit will be kept intact.

4.2.4.2 Unscheduled Visit

Unscheduled visit is visit dimmed as out of schedule by the investigational site. Data collected during unscheduled visits should be handled case by case. The following are some general recommendations:

- Data from unscheduled visit will only be used in listings.
- Data from unscheduled visit might be used to substitute a missing value in a scheduled visit as long as it is authorized and appropriately documented by the medical monitor.

4.2.5 Major Protocol Violations and Minor Protocol Deviations

All Protocol violations will be recorded but any Major Protocol Deviation will be evaluated by the scientifically responsible person (usually the medical monitor) and the statistician, for the purpose of excluding subjects from the per protocol population, before breaking the blinding.

4.2.6 Unexpected switch of the infusion set

Anytime when the participant switched the use of the study infusion set to other infusion set, it is considered the study infusion set is removed for the corresponding period regardless if the study infusion set is used again or not.

4.3 ANALYSIS (Efficacy) VARIABLES

4.3.1 Baseline Characteristics

Baseline characteristic variables such as demographics are captured in the EDC. No conversion will be done unless specified.

If age is captured in the EDC, the reported Age will be used. Otherwise, age can be calculated as

- Age = (date of randomization - Date of birth) / 365.25, if Day is catured
- Or Age = (Year of randomization x 12 + Month of randomization - Year of birth x 12 - Month of birth) / 12, if Day is catured due to privacy concern

Age will be calculated in years with decimal points for more accurate results.

4.3.2 Efficacy Variables

4.3.2.1 Handling of (Possible) Multiple Peaks of GIR and Insulin Curve.

We expect the GIR and insulin curve to have a single peak. However, it is possible that multiple peaks or no peak will be observed. The following are ways to handle GIR curves:

1. Determination of single peak/no peak/Multi-peak will be based on the plot of the GIR/insulin curve
 - a. The statistician will make the judgement based the visual observation of each plot of the GIR/insulin curve
2. No peak. (i.e. the variables keeps rising up to 300 minutes)
 - a. The Maximum, Time to Maximum, Time to Half-Maximum will be set as missing. We will consider these variable as undefined.
 - b. The AUC_{0-t} will be calculated but the $AUC_{0-\infty}$ will be set as missing.
3. Multi-peak.
 - a. If the same Maximum value appears at two or more time point, the Time to Maximum, Time to Half-Maximum will be estimated based on the first occurrence.

All of the following GIR and PK parameters, including the primary variable, will be calculated after this data handling.

4.3.2.2 Handling of (Possible) non-response (0) GIR or Insulin Curve.

It is possible that some subjects do not respond to the bolus insulin which resulted in all GIR to be 0 or Insulin to be 0. In such case, the derived variable of this GIR / Insulin profile will be censored out from all analyses.

4.3.2.3 Variables for Primary Efficacy: Area Under the Curve (AUC) of the Glucose Infusion Rate (GIR)

The variable for Primary Efficacy is the AUC_{0-300} . It is estimated using the methods described in the following section 4.3.2.3.3.

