4.3.2.3.1 GIR_{max}

GIR_{max} will be the maximum GIR readings from time 0 to time 300 minutes.

- In a “No Peak” case, this will be set as missing.

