4.3.2.3.2 Terminal Rate Constant λ

Terminal rate constant λ is needed before we estimate AUC_{0-t} . It is estimated by:

- a. Find the GIRs after GIR_{max} (section 4.3.2.3.1)
 - i. If there only 1 or 0 available GIR reading after GIR_{max} , then λ will be set as missing.
- b. Do a regression of log-transformed GIR vs Time
- c. λ is the slope from this regression
- d. In a “No Peak” case, λ will be set as missing

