4.3.2.3.3 AUC_{0-t}

The AUC_{0-t} of GIR over wear time will be calculated using trapezoid rule and the actual time points. Missing data for the calculation of the AUC will be handled as followed:

1. If the reading for Time 0 is missing, it will be the average of up to 3 prior readings. However, if there is no prior readings available, it will be assumed to be 0
2. If the reading at (actual) time t ($t < 300$ min) is missing, it will be imputed with linear interpolation
3. If the reading at $t=300$ min is missing:
 - a. The reading at $t=300$ min will be imputed using the regression line obtained when estimate λ (section 4.3.2.3.1).
 - b. If λ is missing, AUC_{0-t} will be set as missing.

4.3.2.3.4 $AUC_{0-\infty}$

$AUC_{0-\infty}$ is estimated as

$$AUC_{0-\infty} = AUC_{0-last} + AUC_{last}, \text{ where } AUC_{last} = GIR_{last}/\lambda$$

If λ is missing, then $AUC_{0-\infty}$ is set as missing.

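### The SAP decides by eye, with no masking stated, which GIR and insulin curves have a peak; this governs entry to the secondary PK/PD tests and reaches the primary AUC only in a narrow case

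*SAP*

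**What the plan says.** SAP 4.3.2.1 bases the classification on the plot of each curve and assigns it to one person: "The statistician will make the judgement based the visual observation of each plot of the GIR/insulin curve". The definition reads "No peak. (i.e. the variables keeps rising up to 300 minutes". No tolerance, smoothing rule, second reader or masking step is given. For ties, the first occurrence of the maximum is used.

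The consequences of a no-peak call are spread over several sections:

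- 4.3.2.1, item 2a: "The Maximum, Time to Maximum, Time to Half-Maximum will be set as missing".
- 4.3.2.1, item 2b: begins "The AUC_{0-t} will be calculated but the" and then makes AUC0–∞ missing.
- 4.3.2.3.1 repeats the rule for GIRmax. 4.3.2.4.1 and 4.3.2.4.2 pass a missing GIRmax on to tmax(GIR) and the early t50.
- 4.3.2.3.2, item d: in a no-peak case, "λ will be set as missing". Item a.i of the same section makes λ missing whenever at most one reading follows the maximum, whatever the visual call.
- 4.3.2.5.6 to 4.3.2.5.8 carry the GIR methods over to Cmax, Tmax and t50 for insulin.

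Section 4.3.2.1 closes by saying that all GIR and PK parameters, "including the primary variable, will be calculated after this data handling". The route to the primary variable is 4.3.2.3.3, item 3, which covers a missing 300-minute reading. The value is imputed from the λ regression, but the clause opening "If λ is missing" (item 3b) makes AUC0–t missing.

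The SAP (Study Design) and Protocol 4.1 call the trial open. Protocol 6.3 lists only the randomized sequence and the washout as measures against bias.

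**The concern.** Whether a profile contributes to a between-set comparison should follow from a rule that two analysts would apply identically. Here it follows from one person's reading of a plot. The documents do not say that the plot hides the infusion set.

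GIR is reset by a dosing calculator at each glucose reading (Protocol 6.1.1.5), so stepped curves, plateaus and late drifts are plausible, and readers can disagree about such shapes. GIRmax, tmax(GIR), t50, Cmax and tmax are all tested for treatment effects at α = 0.05 (SAP 4.4.4.2.2 and 4.4.4.2.3). Missing values are not imputed unless specified (SAP 4.2.1), so a no-peak call takes the profile out of those tests. If calls differed by set, even unintentionally, the comparisons would rest on selected profiles. With so few participants, each call carries weight.

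**Working it through.** The plan states no figure to reproduce, so the check traces the rules and then counts profiles.

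**Rule trace.** Inputs are SAP 4.3.2.1 items 2a and 2b, 4.3.2.3.2 items a.i and d, and 4.3.2.3.3 item 3. Where items 2b and 3b disagree, the trace takes 3b as governing.

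| Case | 300-minute reading | Readings after maximum | Visual call | λ | Primary AUC0–300 | GIRmax, tmax, t50 |
|---|---|---|---|---|---|---|
| A | present | any | no peak | missing | calculated | missing |
| B | missing | 0 or 1 | either | missing by the count rule | missing | depends on the call |
| C | missing | 2 or more | peak | estimated | calculated after imputing the 300-minute value | calculated |
| D | missing | 2 or more | no peak | missing by the call | missing | missing |

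- Case A is the ordinary one. The primary AUC survives, and only the peak-based parameters, λ and AUC0–∞ are lost.
- In case B the primary AUC is lost, but by an objective count and not by the visual call.
- Judgement alters the primary AUC only between C and D.

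**How narrow C versus D is.** Table 6 of the protocol has glucose readings every 10 minutes late in the clamp (260, 270, 280, 290, 300). Assume one GIR value per reading and only the 300-minute value absent. A maximum at 290 leaves 0 later readings and one at 280 leaves 1 (the 290), so λ is already missing. Only a maximum at 270 or earlier leaves at least 2 (280 and 290). The visual call therefore matters for the primary AUC only if such a curve is still judged to have no peak. In that situation the verbal criterion cannot be checked as written, because it refers to a rise up to the time point that is missing.

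**Conflict between the rules.** For a no-peak curve without a 300-minute reading, 4.3.2.1 item 2b says that AUC0–t is computed and 4.3.2.3.3 item 3b says that it is missing. Item 2b gives no way to fill the absent value.

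**Reach in the secondary tests.** No missing reading is needed here. A curve that climbs unevenly and is highest at 300 minutes yields tmax = 300 if called a peak, and nothing if called no peak.

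**Count.** SAP 2.5 reports 7 completers, with 4 clamps planned per set:

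- profiles per set from completers: 7 × 4 = 28 at most
- one call as a share of a set's completer profiles: 1/28 = 3.6%
- one call as a share of a set's completers at one visit: 1/7 = 14%

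Clamps lost to early set failure would raise these shares. Non-completers with at least one clamp, whom the ITT definition admits (SAP 4.1.2), would lower them.

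**The case against.** The strongest reply is that the step is harmless in practice. A written definition exists. A maximum is genuinely undefined within the window if the curve is still rising when observation stops, and the SAP says as much. AUC0–t is expressly kept, and so is duration of action, which is AUMC0–300 divided by AUC0–300, when the 300-minute reading exists. The clamp endings before 300 minutes foreseen in Protocol 6.1.1.5 leave GIR at zero, which is the opposite of a rising curve. That leaves only unplanned loss of the last reading. The SAP also plans a sensitivity analysis for missing AUC0–300 (4.4.4.1).

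Most of this stands, and it is why the route to the primary endpoint is narrow. It does not answer the point about the secondary parameters: the verbal definition does not settle plateaus or noisy late rises.

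A reader might also infer three stronger things:

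- **That the statistician is unmasked.** The open design makes this possible, but no document says it. SAP 4.2.5 and the opening of Protocol section 9 both speak of unblinding. Those passages concern per-protocol exclusions and the timing of the SAP, so they do not establish masking of the curve review either. The supportable statement is that no masking is described for this step.
- **That the call biases the comparison in a known direction, because late-rising curves reflect poor absorption.** The documents do not show this. Protocol 2.2.3 describes a seven-day wear study in which tmax was still shortened at day 7 while four-hour exposure was about 21% lower.
- **That 56 profiles (7 × 8) is an upper bound.** It counts completers only, and the ITT population can include others.

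**Conclusion.** The concern holds in a limited form. A by-eye classification, with a verbal criterion and no stated masking, decides which profiles have a GIRmax or Cmax, tmax and t50, and so which enter several secondary PK/PD tests. A reproducible rule is available at almost no cost.

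It would go too far to say that the call generally threatens the primary endpoint. That requires a missing 300-minute reading together with a no-peak call on a curve with two or more readings after its maximum, taking 4.3.2.3.3 item 3b as governing. If item 2b was meant to govern, the call would not remove the primary AUC at all.

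The 3.6% share per call measures leverage, not bias. It assumes that all 7 completers contribute 4 clamps per set. How often such calls would arise, and which set they would favour, cannot be determined from the documents. Priority: minor, mainly for the secondary endpoints.

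**What to change.** Make three changes to the SAP before the curves are classified:

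1. In 4.3.2.1, replace the visual judgement with an algorithm. A curve has no peak if its maximum occurs at the last observed time point. Otherwise it has a peak and the first maximum is used, as the SAP already does for ties. Under this rule every no-peak curve has 0 readings after its maximum, so λ is already missing by the count rule and no discretion over the primary AUC remains.
2. If any visual check is kept, do it on plots without set, period, day or participant labels, before treatment codes are attached.
3. Reconcile 4.3.2.1 item 2b with 4.3.2.3.3 item 3b by stating one rule for AUC0–300 when a no-peak curve lacks its 300-minute reading. The algorithm alone does not settle this.

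The cost is a few sentences, and manual work falls. The downside is that a noisy plateau whose highest value happens to be the last reading is automatically classed as no peak. That is an acceptable price for a rule that treats both sets alike.

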³ Vital signs include BP (seated or recumbent), pulse, respiratory rate and temperature; VS should be done every 2 hours ± 30 min during clamp procedures

⁴ Ascensia Contour Next glucose monitor and Precision Xtra blood ketone monitor with respective test strips will be provided.

⁵ 100 mm Visual Analog Scale (VAS) pain assessment to be performed at Achilles infusion set insertion, daily during home wear period, and at time of Achilles infusion set removal.

⁶ End-of-Study (EOS) and Early Termination (ET) Assessments; if participant terminates early because of cannula failure event then glucose clamp will not be done if failed cannula has been removed. Study completion time may differ per participant. Study is considered complete at the end of the second wear period as determined by: **(1) Participant has worn Achilles infusion sets for 7 days, (2) Participant experiences Achilles set failure requiring change out to commercial CSII set, (3) Participant has hyperglycemic event requiring at home change out to commercial CSII set, or (4) Resolution of device or procedure-related AEs.**

⁷ Blood for clamping decisions every 5-15 min for 300 min

⁸ Meal and individually determined bolus dose of insulin delivered via pump bolus performed in clinic; participants may be discharged home shortly after meal is completed. The same meal and insulin bolus dose (unless clinically indicated that bolus dose should be modified) to be provided for each participant after all clamp studies

⁹ Insertion Site Evaluations for each wear period: Day 0 pre-infusion set insertion and after securing post-insertion; Daily during Day 0 to +7 wear period; Day 7 (or upon infusion set failure) pre-infusion set removal, post-infusion set removal. The site personnel will perform photographic documentation of the insertion site at the time of insertion and at the time of presentation to the study site at the end of each wear period.

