6.1.1.8 STUDY TESTING COMPLETION

Discontinuation from the study intervention (infusion of insulin through a CSII catheter) does not mean discontinuation from the study, and remaining study procedures should be completed as indicated by the study protocol. The need to discontinue clinical use of the investigational or commercial CSII catheter prior to Visit 4A/Visit 4B is expected in some study participants and is not considered an adverse event. If an unplanned change-out of either the Achilles investigational cannula or control CSII set is required during a study visit/clamp, participant’s study participation in the respective treatment phase is considered completed at the time of infusion set change. If change-out occurs during *Treatment Phase 1*, the participant is asked to return for *Treatment Phase 2* after the washout period. If change-out occurs during Treatment Phase 2 the participant should return to the study site for a final study visit.

Before the study participant can be exited from the protocol, the following evaluations must be completed:

- Inspect/photograph insertion site
- Collect patient diary/photos

After completion of final evaluations, participant may be exited from the study.

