9.4.2 ANALYSIS OF THE PRIMARY EFFICACY ENDPOINT(S)

The $\ln(\text{AUC}_{0-300(\text{GIR})})$ on DOI (day 0) and days 3, 5, 7, periods 1 and 2 will be calculated using the trapezoidal rule. A mixed-effects (repeated-measures) linear model with treatment and period as fixed effects and participant as a random effect will then be fit to this data. Estimates of the slopes by treatment will be generated as contrasts based on the least squares means. Treatment comparisons and confidence bounds on the difference in slopes will be presented. Details will be provided in the Statistical Analysis Plan

The natural log of each AUC mean slopes for the two treatment groups will be compared in a mixed-effects (repeated-measures) linear model with treatment and period as fixed effects and participant as a random effect.

The primary analysis will be conducted on the ITT population; the mixed-effects model accounts for missing data using a missing at random (MAR) assumption, which will be checked.

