4.4.4 Efficacy analyses

4.4.4.1 Analyses of Primary Endpoints

Our primary endpoint is the failure rate of infusion set. A descriptive summary of infusion set failures will be provided. The summary will be reported for each period.

The $AUC_{0-300(GIR)}$ on day of insertion (day 0) and days 3, 5, 7 in periods 1 and 2 will be calculated using the trapezoidal rule as described in section 4.3.2.1.

The nature log of AUC: $\ln(AUC_{0-300(GIR)})$ will then be calculated.

A mixed-effects (repeated-measures) linear model with *treatment* and *period* as fixed effects and participant as a random effect will then be fit to this data. Estimates of the slopes by treatment will be generated as contrasts based on the least squares means. The contrast is: the difference in slopes (control minus Achilles) of $AUC_{0-300(GIR)}$ versus day, computed from the least squares means of $AUC_{0-300(GIR)}$ at each study day within each of the 2 periods.

Treatment comparisons and confidence bounds on the difference in slopes will be presented.

The primary analysis will be conducted on the ITT population using all available data within the mixed model repeated measures framework. Missing an $AUC_{0-300(GIR)}$ assessment will be assumed missing at random (MAR). However, a sensitivity analysis will be done to check the extent to which the missing data could have made a difference in the conclusions of the analysis.

Additionally, the same analyses will be repeated on the baseline adjusted AUC_{0-300} and ITT population.

Population	ITT and PP (ITT is the primary , PP is the sensitivity)
------------	---

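### All-zero clamps and clamps missed after set failure never enter the primary slope contrast, so it describes decline only while the set still shows a measurable effect

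*SAP*

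**What the plan says.** - **Objective and endpoint.** Protocol 3.1 and SAP 2.1 ask how fast the glucose-lowering effect declines from day 0 to day 7. The endpoint is the slope of ln(AUC0-300 GIR) over days 0, 3, 5 and 7.
- **All-zero profiles.** SAP 4.3.2.2: "the derived variable of this GIR / Insulin profile will be censored out from all analyses".
- **Missing 300-minute reading.** SAP 4.3.2.3.3: it "will be imputed using the regression line obtained when estimate" lambda. SAP 4.3.2.3.2 obtains lambda thus: "Do a regression of log-transformed GIR vs Time". Without lambda the AUC is missing.
- **Clamps after failure.** Protocol 1.3, footnote 6: "glucose clamp will not be done if failed cannula has been removed". Protocol 6.1.1.8, for a change-out during a visit: "study participation in the respective treatment phase is considered completed at the time of infusion set change".
- **Missing AUCs.** SAP 4.4.4.1: a missing AUC "assessment will be assumed missing at random (MAR"). It adds a sensitivity analysis but names no method. Protocol 9.4.2: "the mixed-effects model accounts for missing data using a missing at random (MAR) assumption, which will be checked".
- **Failure reported separately.** SAP 4.4.4.1 opens with "Our primary endpoint is the failure rate of infusion set" and summarises failures descriptively. There is also a life-table comparison (4.4.4.2.1), time to failure (4.3.2.7.2) and malfunction counts (4.4.5.4).
- **Size.** SAP 2.5: the sponsor ended the study after the 7th completer.

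**The concern.** A set that worked on day 0 and gave no measurable effect on day 7 has shown the steepest decline the endpoint can register. Under these rules its day-0 value stays in the model and its day-7 value does not. A set whose day-7 AUC is very small but positive enters with a strongly negative change. The scale is cut off exactly at its worst end.

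The MAR assumption does the same for sets removed because delivery failed: the model fills the gap from sets that were still working. If one device produces more late zeros or late failures than the other, the contrast will not show it, and that device looks better on the primary outcome than it was. With about 7 completers, a single such clamp can matter.

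**Working it through.** **1. The plan's own figure.** SAP 3.4 states 90% power with 24 participants, slope difference 0.07, total variance 0.21, 40% of it within participant (0.084), AR r = 0.5. The unit of the slope is not stated; I take it as per day. With AR by visit, the SD of a participant's slope difference is 0.0782, the standard error at n = 24 is 0.0782/√24 = 0.0160, and power is 0.99. The 90% is not reproduced, but it is conservative and nothing below depends on it.

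**2. What happens to each kind of late clamp, given a working day-0 clamp**

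| Clamp result | Rule | In the slope contrast? |
|---|---|---|
| Low but non-zero GIR | 4.3.2.3.3 | Yes, as a low ln value |
| Complete clamp, all GIR zero | 4.3.2.2 | No |
| Stopped early for hyperglycemia, no dextrose given | 4.3.2.2; also 4.3.2.3.2 and 4.3.2.3.3, since zeros have no logarithm | No |
| Not done, failed set removed | 4.4.4.1, MAR | No |

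The third row largely repeats the second.

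**3. Slope weights.** Days 0, 3, 5, 7 have mean 3.75 and sum of squares 26.75. The weights (day − 3.75)/26.75 are −0.1402, −0.0280, 0.0467 and 0.1215. I assume treatment-by-day least squares means, as the contrast in 4.4.4.1 requires.

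**4. An illustrative floor.** The lowest dextrose rate in Protocol 6.1.1.5 is 0.1 mg/kg/min, and 0.1 × 300 = 30 mg/kg. Against a day-0 mean GIR of 0.5, 1, 2 or 4 mg/kg/min (assumed; 4 is the top of the protocol range), that is 20%, 10%, 5% or 2.5% of the day-0 AUC. The drops on the ln scale are 1.609, 2.303, 2.996 and 3.689.

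**5. One affected set among 7, compared with no decline in that set**

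- Day 7 only: 0.1215 × 2.303/7 = 0.040 per day. For the other floors: 0.028 (20%), 0.052 (5%), 0.064 (2.5%).
- Days 5 and 7: 0.1682 × 2.303/7 = 0.055.
- Days 3, 5 and 7: 0.1402 × 2.303/7 = 0.046.
- Day 3 only, then working again: 0.0280 × 2.303/7 = 0.009 in the opposite direction.
- Day-3 zero floored but later clamps left MAR: 0.001 (random intercept) to 0.016 (AR), against 0.046 when the later clamps are floored too. Flooring observed zeros alone therefore misses most of an early removal.

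**6. Assumed rates of day-7 zeros, 10% floor**

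- Control 30%, Achilles 10%, equal working slopes: floored contrast 0.1215 × 0.20 × 2.303 = 0.056 per day; with deletion 0.000 (simulated).
- Working Achilles sets 0.07 per day better, but zeros in 30% of Achilles and 10% of control sets: 0.07 − 0.1215 × 0.30 × 2.303 + 0.1215 × 0.10 × (2.303 − 0.49) = 0.008, where 0.49 = 7 × 0.07. The range is 0.025 to −0.026 for floors of 20% to 2.5%. Deletion still gives 0.07.
- True difference 0.07, zeros in 30% of both arms: 0.07 − 0.1215 × 0.30 × 0.49 = 0.052. Equal rates leave the contrast unchanged only if the working slopes are equal.

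**7. What the floor costs (simulation, n = 7, SAP variances, 10% floor).** With 30% day-7 zeros in both arms and no true difference, the SD of the contrast rises from about 0.03 to about 0.075. A plain random-intercept model rejects in 12% of trials; a paired t test on within-participant slope differences rejects in 4 to 5%. With a true 0.07, the paired test rejects in 12%, against 51% with no zeros.

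**The case against.** **All-zero GIR is not proof of complete loss.** This stands. Protocol 6.1.1.5 starts dextrose only when glucose is 5 mg/dL below baseline, so a weakened bolus that merely offsets rising glucose also gives GIR zero. Protocol 4.3 and 6.1.1.5 also allow IV insulin during the clamp. The value is low and left-censored; calling it total failure goes beyond the documents.

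**Deletion is right for a different question.** This also stands. For slopes while the set works, deletion returns the true value in simulation. A reader might infer that the contrast is biased under any reading, but that does not follow. It falls short for overall decline from day 0 to day 7, which is how the objective is worded.

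**Failure is analysed elsewhere.** It is, so the plan does not hide failures. A zero-GIR clamp with measurable insulin may also remain in the PK analysis. None of this alters the slope result. A zero-GIR clamp also need not count as a failure: both glucose-based criteria in Protocol 7.1.1 need more than 250 mg/dL. From 95 mg/dL, without IV insulin, that means an average rise of (250 − 95)/300 = 0.52 mg/dL per minute over the clamp.

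**A sensitivity analysis is planned.** It has no stated method, and read literally 4.3.2.2 would remove the zeros from it too.

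**ln(0) is undefined.** Some rule is therefore needed, but deletion is not the only one available.

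**Every rate is assumed.** True. The SAP says only that zero profiles are possible.

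**Conclusion.** The point holds in limited form. SAP 4.3.2.2 and the MAR rule in 4.4.4.1 keep the lowest values of the primary outcome out of the slope contrast, including loss of effect after a working day-0 clamp. The result describes slopes only while the set shows a measurable effect. If late zero or failed clamps differ by device, it misstates overall decline in favour of the device that loses effect more often.

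A reader might infer that the rules favour Achilles. The documents do not support that: they give no zero-GIR rates by device, and the direction depends on which set loses effect more. The statement also does not extend to day-0 zeros, whose weight is negative: flooring one would make the failing set look better.

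The size is about 0.040 per day for one day-7 zero among 7 sets (0.028 to 0.064), more than half the design difference of 0.07 at the 10% floor. This rests on an assumed floor, a per-day slope and 7 sets per arm. The ITT population needs only one completed clamp, so it may hold more sets and the shift per set may be smaller. It should be fixed; confidence is medium.

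**What to change.** 1. **SAP 4.3.2.2, GIR AUC.** Keep every all-zero clamp on day 3, 5 or 7 from a set with a non-zero day-0 clamp, as left-censored at one pre-stated floor, whichever way it moves the contrast. An example is 30 mg/kg, with 15 and 60 as sensitivity values. State how a measured non-zero AUC below the floor is treated. Exclude only documented technical clamp failures. Flag clamps with IV insulin after the bolus and analyse with and without them. Clamps stopped early for hyperglycemia with no dextrose follow the same rule.
2. **Day-0 zeros.** These sets have no measurable decline. List them by device beside the set-failure results.
3. **SAP 4.4.4.1.** Name the sensitivity analysis: clamps missed after a delivery-type failure (unresponsive hyperglycemia, hyperglycemia with ketones, non-resolvable occlusion) that follows a working day-0 clamp take the same floor, with a tipping-point range. Other missing clamps stay MAR.
4. **Test.** Pre-state one method for the floored contrast that does not rely on plain random-intercept standard errors, such as a paired t test on within-participant slope differences. Say how participants without a slope in both periods are handled.
5. **Reporting.** Show the current deletion/MAR result beside it, labelled 'while the set works'. List all zero-GIR and failure-missed clamps by device and day.

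The cost is new wording in two SAP sections (4.3.2.2 and 4.4.4.1) with a cross-reference in 4.3.2.3.3, a few extra runs, and a listing drawn from at most 7 × 8 = 56 clamps for the completers. The floor is a convention and late-day variance rises. At about 7 completers the floored result is an estimate with little power.
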